8.3. Safety evaluation method

There is one primary safety endpoint to be evaluated in this study.

8.3.1. Description of the safety endpoint

Freedom from MRI-scan related complications from the time of the MRI scan to 1-month post-MRI scan testing.

8.3.2. Selection of method and time for evaluation, recording and analysis of the safety endpoints

Since the objective is to evaluate the effect of MRI exposure for the ICD/ CRT-D device groups included in this study, the safety parameters were selected to include only MRI-scan related complications from the time of device programming for an MRI scan to 1-month post-MRI scan. An independent physician CEC will adjudicate all adverse device effects during this period to determine the relatedness to the MRI scan.

Safety surveillance within this study and the safety reporting, both performed by the investigator, starts as soon as the subject completes the pre-MRI visit testing and the MRI Settings have been programmed according to the protocol. The safety surveillance and the safety reporting will continue until the last study visit has been performed, the subject is deceased, the subject/investigator concludes his participation into the clinical study or the subject withdrawal from the clinical study.

8.4. Study procedures

The clinical study will be conducted in accordance with the CIP. All parties participating in the conduct of the clinical study will be qualified by education, training, or experience to perform their tasks and this training will be documented appropriately.

The clinical study will not commence until Abbott receives written approval from the IRB/EC and relevant regulatory authorities and all required documents have been collected from the site(s).

[figure not shown]
Approval from the Sponsor must be received prior to initiating study procedures.

Enrolled subjects (as defined in section **8.4.3**) will have undergone a successful implant procedure with the study ICD/ CRT-D and study leads. Forty-five (45) days after discharge from hospitalization post successful implant procedure, the subject will have a MRI Scan Visit, followed by a one-month post MRI Scan Visit. Upon completion of the one-month post MRI scan visit, the subject will be considered to have completed the follow-up requirements of this clinical study. The Principal Investigator should arrange for appropriate care of subjects following study completion.

The following sections provide a detailed description of procedures required by this CIP.

8.4.1. Study flow chart

FIGURE 2: STUDY FLOW CHART

8.4.2. Patient recruitment

All patients presenting at the study site may be screened by a member of the study team previously trained on the CIP and delegated to do so. Patients who do not meet the inclusion/exclusion criteria will not be eligible to participate in this study. Patients meeting the inclusion/exclusion criteria will be fully informed about the study and asked to review and sign informed consent. In case the subject agrees, a duly signed and dated Patient Informed Consent will be obtained. Qualifying patients will be approached with the study consent at all participating study centers.

8.4.3. Point of enrollment

Subjects are considered enrolled after the study consent has been signed (Refer to section **14.5** for the Informed Consent Process).

The Principal Investigator or delegated study personnel will record enrollment information (name of the clinical investigation, date of consent and Inclusion/exclusion information) in the hospital records and complete and submit an applicable CRF in a timely manner.

Notification of enrollment to the Sponsor is considered to have occurred when the Sponsor has received the applicable CRF.

8.4.4. Scheduled procedures

The Principal Investigator is responsible for ensuring all clinical study data is collected as required per CIP scheduled procedures.

All required study procedures at each specified interval are outlined in the sections below. Refer to **Table 2: Schedule of Evaluations Summary: Study visits**, **Table 3: Schedule of Evaluations Summary: MRI Related visits**, and **Table 4: Subject visit data collection summary** for an overview of the required study procedures at each interval or study visit.

TABLE 2: SCHEDULE OF EVALUATIONS SUMMARY: STUDY VISITS

Evaluation	Cardiology Staff					
	Study Visits					
	Enrollment	Implant	Baseline	MRI Scan	1-month visit	Unscheduled (as necessary)
Time frame from previous visit (window) in days	0	≤ 7 post enrollment	45 (+7) post implant	≤ 14 post Baseline	30 (+14) post MRI Scan	-
Informed Consent	√					
Inclusion/ Exclusion Evaluation	√					
Demographics and Medical History	√					
Verify ICD/ CRT-D and lead combination (group) post-implantation		√				
Pre-MRI Safety Screening (MRI Safety Screening Form)	√		√	√*		
Capture ICD/ CRT-D system information		√				
Device Interrogation/ Device Measurements**			√	√	√	√
Collect Study Specific AEs				√	√	√

* re-verify if not done same day as Baseline

** Capture bipolar capture, sense, pacing, and HVLI impedances

Note: RA lead capture only for subjects with Tendril STS or Isoflex leads. RA capture and sensing thresholds are not required if a patient is in atrial fibrillation or atrial flutter. If the RA capture and sensing thresholds could not be obtained due to a patient's atrial fibrillation or flutter, and if the patient's atrial fibrillation or flutter is transient, for data analysis purposes, the pacing capture threshold and sensing threshold from the most recent archival measurement, if available, will be used.

TABLE 3: SCHEDULE OF EVALUATIONS SUMMARY: MRI RELATED VISITS

Evaluation	Radiology & Cardiology Staff			
	MRI Visit Schedule			
	MRI visit			1 Month Post MRI
	Pre-MRI Period Testing	MRI Period	Post-MRI Testing	
Re-assess Inclusion/Exclusion Criteria	✓			
Device Interrogation/ Device Measurements*	✓		✓	✓
Pre-MRI Safety Screening (MRI Safety Screening Form)	✓			
MRI Hazard Checklist	✓			
Pregnancy Test	✓			
Pulse Oximetry (optional)		✓		
ECG		✓		
Save MRI Setting	✓			
Activate MRI Setting		✓		
Deactivate MRI Setting			✓	

* Capture bipolar capture, sense, pacing, and HVLI impedances

Note: RA lead capture only for subjects with Tendril STS or Isoflex leads. RA capture and sensing thresholds are not required if a patient is in atrial fibrillation or atrial flutter. If the RA capture and sensing thresholds could not be obtained due to a patient's atrial fibrillation or flutter, and if the patient's atrial fibrillation or flutter is transient, for data analysis purposes, the pacing capture threshold and sensing threshold from the most recent archival measurement, if available, will be used.

TABLE 4: SUBJECT VISIT DATA COLLECTION SUMMARY

Study Visit	Visit Window	Study Procedures and Data Collection
Enrollment	Up to or same day before Implant	
 Screen patient for enrollment eligibility Obtain informed consent Obtain medical and surgical history Collect demographic information Document indication for implant of ICD/ CRT-D

Study Visit	Visit Window	Study Procedures and Data Collection
		
 Determine ICD/ CRT-D and lead combination (group) for the subject to be implanted
Implant	
No greater than 7 days after enrollment visit
 
Re-attempt scheduled at time of discharge (if applicable)
	
 Implant ICD/ CRT-D and leads within 7 days of obtaining consent Obtain ICD/ CRT-D system information: model and serial number of implanted ICD/ CRT-D system If implant is unsuccessful and no re-attempt to implant is attempted subject should be withdrawn from the study If implant is unsuccessful and re-attempt to implant is attempted subject should continue in the study to the MRI Scan Visit 45(+7) days from the successful implant date.
Baseline/ MRI Scan Visit	
45 (+7) days after implantation or after most recent lead revision
 
MRI scan should occur within 14 days of Baseline visit.
 
The pre-MRI scan, MRI, and post MRI scan procedures should occur on the same day.
	
Pre-MRI Scan testing
 
 Assess inclusion/exclusion criteria Screen, clear and prep subject for MRI scan Complete MRI screening form Complete MRI Hazard Checklist Administer pregnancy test – can be done up to 7 days before MRI scan Interrogate device Perform capacitor maintenance Obtain in-clinic lead measurements: bipolar capture, sense, pacing and HVLI impedances^{1,2} Setup and activate MRI Settings 
During MRI Scan
 
 Monitor subject with ECG, or pulse oximetry, and verbal communication 
Post-MRI scan testing
 
 Interrogate device Deactivate MRI Settings Obtain in-clinic lead measurements: bipolar capture, sense, pacing and HVLI impedances^{1,2} Evaluate subject for any adverse events (serious and non-serious) and submit an AE CRF (as applicable). Report deviations, screening failure/withdrawal and out of service as applicable Submit MRI scan results, e.g. scan time, sequences used, etc. Upload device session records through the EDC study site portal
1-Month Post MRI Scan Visit	30 days after MRI scan (0/+14 days)	
 Interrogate device Obtain in-clinic lead measurements: bipolar capture, sense, pacing and HVLI impedances^{1,2}

Study Visit	Visit Window	Study Procedures and Data Collection
		
 Evaluate subject for any adverse events and submit an AE CRF (as applicable). Report deviations, withdrawal and out of service as applicable Upload device session records through the EDC study site portal
System Revision (if applicable)	Can occur any time after implant	
 Interrogate device Obtain applicable in-clinic lead measurements: bipolar capture¹, sense², and pacing and HVLI impedances for cases where the lead was repositioned, or was replaced with another Durata/Optisure or Tendril/Isoflex, Quartet lead, or where the ICD/ CRT-D was replaced with another Ellipse ICD/ Quadra Assura MP CRT-D. Evaluate subject for any adverse events and submit an AE CRF (as applicable). Report deviations, withdrawal and out of service as applicable Upload device session records through the EDC study site portal
Unscheduled (if applicable)	Any time after the MRI scan visit before the 1 Month Post MRI Scan Visit	
 Interrogate device. Obtain applicable in-clinic lead measurements: bipolar capture, sense, pacing and HVLI impedances^{1,2} If an unscheduled visit occurs prior to the 1-month post MRI visit, evaluate subject for any adverse events and submit an AE CRF (as applicable). If an unscheduled event occurs after the 1-month post MRI visit, then the AE events do not need to be submitted in CRF, instead device-related AEs must be reported to the Sponsor as per vigilance/commercial reporting requirements. Report deviations, withdrawal and out of service as applicable Upload device session records through the EDC study site portal

8.4.4.1. Enrollment

Consider all patients for participation in this study regardless of gender. Screen patients as outlined by the inclusion/exclusion criteria. Obtain informed consent from the patient.

Obtain demographic, medical, and surgical history. Document indication for the ICD/ CRT-D system to be implanted and determine ICD/ CRT-D lead combination to be implanted. The principal investigator or delegated study personnel are responsible for screening all potential subjects to determine subject eligibility for the study and for

determining the ICD/ CRT-D lead combination (study group) for the subjects. This visit may occur up to or on the same day as the implant visit. The study implant ICD/ CRT-D and leads will be implanted within 7 days of obtaining consent.

8.4.4.2. Implant

Perform the device and lead implant procedure according to standard of care. Consult the User's Manual for implantation guidelines, appropriate lead/device connections and general handling information. The ICD/ CRT-D system will be considered successfully implanted if; at a minimum, the Ellipse VR/ DR, or Quadra Assura MP generator and a Durata, Optisure, Tendril STS, Isoflex, or a Quartet lead are implanted according to the study group for the subject.

Unsuccessful Implant- if applicable

Enrolled subjects who have an unsuccessful implantation of the study device and lead (see definition for successful implant above) will be withdrawn from the study unless the implant will be re-attempted and is scheduled at the time of discharge. The physician may re-attempt the implantation of study devices at his/her discretion.

8.4.4.3. Baseline and MRI scan visit

The Baseline visit must occur the latter of:

- ≥45 days after lead implant AND
- ≥45 days after most recent lead revision, if applicable

The MRI Scan Visit should occur ≤14 days after the baseline visit or may be performed on the same day as the Baseline visit.

To ensure the patient meets the requirements to undergo the study MRI scan, use the MRI Screening Form for reverification. Prior lead measurements performed at the Baseline visit may be used to evaluate inclusion criteria at the MRI visit.

The MRI visit is composed of 3 sections: Pre-MRI Scan Testing, MRI scan, and Post-MRI Scan.

IMPORTANT NOTE: Before the MRI Scan Visit, if the subject underwent a system revision since enrollment that resulted in:

- implant of a non-study generator or lead, or
- capping/abandoning of a lead
- implant of a non-MRI compatible device or material, or
- any combination above

The subject is no longer eligible to undergo the study MRI Scan. Do not proceed with any of the tests listed for the MRI Scan Visit. The subject should be withdrawn. Refer to section **8.4.5** for further details.

Otherwise, follow the procedures outlined below for the MRI Scan Visit.

8.4.4.4. Pre-MRI scan testing

Pregnancy Testing

Administer a pregnancy test (per institutional standard) to all female subjects of childbearing potential. The pregnancy testing may be done up to 7 days before the MRI scan. Document the results of the test. If the subject is pregnant, do not proceed any further. The subject should be withdrawn.

Clearing the Subject for the Study Scan

To safely perform an MRI scan on a subject with the implanted study system, the physician/clinician should do the following as stated in the MRI Procedure Information for the St. Jude Medical® MR Conditional defibrillation system:

- Confirm that the patient has an MR Conditional System
- Confirm that no adverse conditions to MRI scanning are present (e.g. additional hardware)
- Review the potential adverse events
- Generate a report of the patient's permanently programmed parameters
- Select and Save MRI Settings
- Review the MRI Checklist and Program the MRI Settings using the Merlin® PCS
- Subject receives the MRI Scan
- Disable MRI Settings Using the Merlin® PCS

The radiologist or staff, a designated radiological member, must determine the subject's eligibility for an MRI scan prior to the MRI scan (per standard of practice). However, the ICD/ CRT-D and lead (wires) contraindication item on the MRI hazard checklist do not apply if the subject is implanted with any one of the four main device systems included in this study.

The study MRI Hazard Checklist may be used to document a radiologist or designated member of the radiology department has cleared the subject for an MRI scan.

Alternatively, the radiology department may use its own hazard checklist in lieu of the study MRI Hazard Checklist. This documentation should be maintained with the subject's medical and/or study records.

Device Assessment and Programming

Interrogate the ICD/ CRT-D and obtain the following for the Study leads:

- In-clinic bipolar and unipolar* capture threshold at a pulse width of 0.5 ms. Either the manual decrement or automatic (in-clinic, programmer-based) method may be used to obtain the capture threshold.
Note: If the capture threshold is $> 2.5V$ at 0.5ms for RA and RV leads or $> 2.0V$ at 0.5 ms for LV leads, then the subject does not meet pre-MRI screening criteria.
- In-clinic bipolar sensing amplitude. Either the incremental or the automatic (in-clinic, programmer based) method may be used to obtain the sensing threshold.
Note: If the ventricular sensing is not measurable (patient has underlying rhythm $< 30bpm$) and the sensing amplitude is $< 4mV$, then the patient does not meet pre-MRI screening criteria.
- In-clinic atrial and ventricular bipolar and unipolar* lead impedance

***NOTE:** *Unipolar and bipolar configurations should be collected for LV leads*

NOTE: *RV capture thresholds are not required to be obtained if a high ventricular rate is present (e.g. 110bpm). If available, sites should use the automatically obtained pacing capture threshold from the most recent archival data as a substitute for the in-clinic capture threshold. RV sensing measurements are not required if the subject's intrinsic rate has been established to be ≤ 30 beats per minute.*

If the device testing results do not meet the MRI conditions for scanning per the MRI Procedure manual (also see below), or the patient's sensing threshold is not measurable or the sensing threshold is less than 4mV, the physician may choose to reschedule the subject to return for re-testing. The subject's 1 Month Post MRI Scan Visit will need to be rescheduled to correspond with the MRI Scan Visit where the MRI scan was completed.

Review the MRI checklist on the programmer. Verify the following conditions before saving the MRI Setting.

- Bipolar capture thresholds are stable at $\leq 2.5V$ @ 0.5 ms for RA and RV leads or $> 2.0V$ @ 0.5ms for LV leads.
- Bipolar pacing lead impedance is within range, i.e. ≥ 200 and ≤ 2000 ohms
- HVLI is within range, i.e. ≥ 20 and ≤ 200 ohms
- No additional hardware (adaptors, extenders, or abandoned leads)

Save the MRI Setting after the MRI Checklist has been reviewed, using the parameters listed in **Table 5** for ICDs and **Table 6** for CRT-Ds. Perform all other applicable tests and procedures.

TABLE 5: MRI PARAMETERS-ICD

Parameters	Selectable Options	Nominal Values
MRI Mode*	VOO Pacing Off	Pacing off
MRI Base Rate	30-100 bpm, in steps of 5 bpm	n/a

Parameters	Selectable Options	Nominal Values
MRI RV Pulse Configuration	Bipolar	n/a
MRI RV Pulse Amplitude	5.0 V, 7.5 V	n/a
MRI RV Pulse Width	1.0 msec	n/a
Tachy settings	Disabled	Disabled

*Note: When MRI Settings are enabled, sensing is disabled. Determine whether or not the subject requires pacing support during the MRI scan. When pacing support is needed, set the MRI Mode to the asynchronous pacing mode (VOO). When pacing support is not needed, set the MRI Mode to Pacing Off.
 
Some subjects may be susceptible to cardiac arrhythmia induced by competitive pacing when an asynchronous MRI Mode is selected. For these subjects, it is important to select an appropriate MRI pacing rate to avoid competitive pacing and then minimize the duration of the asynchronous pacing operation.
 
In MR Conditional ICDs, tachytherapy is disabled when the MRI settings are programmed. After the electrical measurements for the RA lead and/or RV lead have been taken, capacitor maintenance has been performed, the MRI Checklist (on the programmer) verified and the MRI Setting saved, activate the MRI parameters.
		

TABLE 6: MRI PARAMETERS- CRT-D

Parameters	Selectable Options	Nominal Values
MRI Mode*	DOO Pacing off	DOO
MRI Base Rate	30-100 bpm	85 bpm
MRI paced AV delay	25-120ms	120 ms
MRI RV Pulse Configuration	Bipolar	n/a
MRI RV Pulse Amplitude	5.0 V, 7.5V	n/a
MRI RV Pulse Width	1.0 msec	n/a
MRI V pacing chamber	RV only	RV only
Tachy settings	Disabled	Disabled

*Note: When MRI Settings are enabled, sensing is disabled. Determine whether or not the subject requires pacing support during the MRI scan. When pacing support is needed, set the MRI Mode to the dual chamber asynchronous pacing mode (DOO).
 
Some subjects may be susceptible to cardiac arrhythmia induced by competitive pacing when an asynchronous MRI Mode is selected. For these subjects, it is important to select an appropriate MRI pacing rate to avoid competitive pacing and then minimize the duration of the asynchronous pacing operation.
 
In MR Conditional CRT-Ds, tach therapy is disabled when the MRI settings are programmed.
 
After the electrical measurements for the RA lead and/or RV lead, and/or LV lead have been taken, capacitor maintenance has been performed, the MRI Checklist (on the programmer) verified and the MRI Setting saved, activate the MRI parameters.
		

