2.2. Primary Endpoints

- Safety: Freedom from MRI-scan related complications related to the ICD/ CRT-D device and/or leads from the time of the MRI scan to 1-month post-MRI scan testing.
- Effectiveness: Proportion of leads with a capture threshold increase of $\leq 0.5V$ at 0.5ms for RA and RV leads and $\leq 1.0V$ at 0.5ms for LV leads from pre-MRI scan to 1-month post-MRI scan testing.
- Effectiveness: Proportion of leads with a sensing amplitude decrease of $\leq 50\%$ from pre-MRI scan testing to 1-month post-MRI scan.

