8.4.4.7. One (1) month post scan visit

8.4.4.7.1. Testing

Interrogate the ICD/ CRT-D and obtain electrical lead measurements.

- In-clinic bipolar and unipolar* capture threshold at a pulse width of 0.5 ms. Either the manual decrement or automatic (in-clinic, programmer based) method may be used to obtain the capture threshold. If a significant rise in pacing threshold ([contact] or greater) from pre-MRI scan to one-month post MRI scan has occurred, then complete an AE form.
- In-clinic bipolar sensing amplitude. Either the incremental or the automatic (in-clinic, programmer based) method may be used to obtain the sensing threshold.
- In-clinic atrial and ventricular bipolar and unipolar* lead impedance
- Evaluate the subject for ADE and SADE and submit an AE CRF- if applicable.

***NOTE:** *Unipolar and bipolar configurations should be collected for LV leads*

NOTE: *RV capture thresholds are not required to be obtained if a high ventricular rate (e.g. 110bpm) is present. If available, sites should use the automatically obtained pacing capture threshold from the most recent archival data as a substitute for the in-clinic capture threshold. RV sensing measurements are not required if the subject's intrinsic rate is established to be ≤ 30 beats per minute.*

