1.4.2 Primary Effectiveness Endpoints

- #1: Proportion of leads with a capture threshold increase of $\leq 0.5V$ at 0.5ms for RA and RV leads and $\leq 1.0V$ at 0.5ms for LV leads from pre-MRI scan to 1-month post-MRI scan testing.
- #2: Proportion of leads with a sensing amplitude decrease of $\leq 50\%$ from pre-MRI scan to 1-month post-MRI scan testing.

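### The capture and sensing test method is left open at every visit, so a lead's pre-scan and 1-month values may come from different methods; a same-method rule would be a cheap improvement

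*Combined protocol and SAP*

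**What the plan says.** Protocol 8.4.4.4 (pre-MRI scan testing) says of capture: "Either the manual decrement or automatic (in-clinic, programmer-based) method may be used to obtain the capture threshold". For sensing it says: "Either the incremental or the automatic (in-clinic, programmer based) method may be used to obtain the sensing threshold". Section 8.4.4.6 (same-day post-scan testing) gives both permissions again. Section 8.4.4.7.1 (1-month visit) repeats the capture wording, "Either the manual decrement or automatic (in-clinic, programmer based) method may be used to obtain the capture threshold", and the sensing wording, without referring back to the method used before the scan.

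Two notes admit a third source of values. With a high ventricular rate, for RV capture, "sites should use the automatically obtained pacing capture threshold from the most recent archival data as a substitute for the in-clinic capture threshold". For the RA lead in transient atrial fibrillation or flutter, the notes to Tables 2 and 3 say that "the pacing capture threshold and sensing threshold from the most recent archival measurement, if available, will be used".

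The endpoints that use these readings are in protocol 2.2 and 8.2.1 and in SAP 1.4.2 and 2.3.2. The first is the "Proportion of leads with a capture threshold increase of" at most 0.5 V for RA and RV leads and at most 1.0 V for LV leads, both at 0.5 ms. The second is the proportion of leads whose sensing amplitude falls by no more than 50%. Both run from pre-scan to 1 month. Protocol 14.2 relies on each subject serving as their own control and concludes that confounding is not a concern for effectiveness.

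**The concern.** A within-lead comparison removes stable differences between patients and leads. It does not remove a change in how the reading is taken. If the two methods read differently on average, a switch between visits adds that difference to the change score, and the change score is then cut at a fixed limit. A switch one way can fail an unchanged lead. A switch the other way can hide a real rise beyond the limit, which matters more in a study asking whether scanning harms lead performance.

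The design offers little to absorb this. The study is single-arm, so no control group shares the offset. Protocol 8.1.12 plans for as few as 10 subjects per group, and SAP 2.6 provides for analysis group by group, so a single misclassified lead is visible in the result.

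**Working it through.** **The plan's own figure.** Protocol 8.1.12 requires 10 subjects per group and allows 5 for attrition in each of 4 groups: 4 × (10 + 5) = 60, as stated. SAP 2.4 says that no sample size calculation or power analysis was done, so there is no power-based number to reproduce, and a same-method rule leaves 60 unchanged.

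**Leads under each limit.** Groups 1 to 4 carry 1, 2, 2 and 3 study leads per subject. At 10 subjects per group that is 10 × (1 + 2 + 2 + 3) = 80 leads. Ten are LV leads with the 1.0 V limit, so the 0.5 V limit applies to 70.

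**Assumptions.** The documents give no measurement error, no manual–automatic difference and no step size. I assume a per-reading SD s of 0.10 to 0.20 V, independent normal errors, and a method offset b of 0.25 V when the method switches. The measured change is then Normal(true change + b, s√2), with an SD of 0.141 V at s = 0.10 and 0.283 V at s = 0.20.

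**False failure of an unchanged RA/RV lead:** P = 1 − Φ((0.5 − b)/(s√2)).

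| Situation | s = 0.10 V | s = 0.20 V |
|---|---|---|
| Same method at both visits (b = 0) | 1 − Φ(3.54) = 0.02% | 1 − Φ(1.77) = 3.9% |
| Every lead switches adversely (b = +0.25) | 1 − Φ(1.77) = 3.9% | 1 − Φ(0.88) = 18.8% |
| Every lead switches the other way (b = −0.25) | 1 − Φ(5.30) ≈ 0% | 1 − Φ(2.65) = 0.4% |
| Each visit's method an independent 50/50 choice | 1.0% | 6.7% |

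In the last row half the leads keep their method and a quarter switch each way. At s = 0.20 this gives 0.5 × 3.9% + 0.25 × 18.8% + 0.25 × 0.4% ≈ 6.7%.

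**In leads, out of 70.** The upper bound is 70 × 0.0385 = 2.7 to 70 × 0.188 = 13.2 failures. With no offset the same model already gives 0.01 to 2.7. Under the 50/50 choice the excess over no offset is 70 × (0.0097 − 0.0002) = 0.7 to 70 × (0.0674 − 0.0385) = 2.0 leads. If sites keep one method the excess is zero.

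**Smaller offset.** With b = 0.125 V and every lead switching adversely, the rate is 0.4% to 9.2%.

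**LV leads.** With b = 0.25 V and the 1.0 V limit, the rate is at most 1 − Φ(0.75/0.283) = 0.4%.

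**A true rise of 0.6 V scored as a success:** P = Φ((0.5 − 0.6 − b)/(s√2)), with b negative when the switch opposes the rise.

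| Situation | s = 0.10 V | s = 0.20 V |
|---|---|---|
| No offset | Φ(−0.71) = 24% | Φ(−0.35) = 36% |
| 50/50 choice at each visit | 34% | 38% |
| Every switch opposes the rise (b = −0.25) | Φ(1.06) = 86% | Φ(0.53) = 70% |

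**What one lead does to a reported result.** With exact 95% Clopper–Pearson intervals, which SAP 2.2.2 says may be presented, one failure among 10 leads of one type moves the proportion from 100% (69.2–100) to 90% (55.5–99.7). Among 70 RA/RV leads it moves from 100% (94.9–100) to 98.6% (92.3–100).

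I have put no figure on sensing. The same mechanism applies, but a 50% relative limit would need a further assumption about how far the methods differ proportionally.

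**The case against.** The strongest reply is that the effect may be small or absent. Nothing in the documents shows that the methods read differently, and sites may well keep to one method from habit. The larger figures need every lead to switch and always in the same direction. That stands, and those figures are bounds rather than forecasts.

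The analysis is also descriptive, with no hypothesis test and no success criterion (SAP 2.2, 2.4, 2.7), so neither type I error nor power is at stake. That lowers the severity. It does not remove the question of whether the two readings are comparable, since these proportions are the primary effectiveness evidence for the labelling application.

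A reader might infer four stronger things that the documents do not support:

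- **That the 0.5 V limit governs every reading.** It covers RA and RV capture only.
- **That sites could pick a method to reach a result.** The study is open-label, but nothing suggests such intent. Protocol 8.2.2 has values recorded directly from the device, and session records are uploaded. An unplanned switch is enough for the concern.
- **That the method is neither recorded nor handled in the analysis.** Much of SAP 2.3.2 is redacted and the case report forms are held separately, so this cannot be known. Hidden analysis text could not, however, make readings comparable once sites had used different methods.
- **That the electrode configuration is also left open.** Bipolar capture at 0.5 ms and bipolar sensing are specified at all three tests, with unipolar readings additional for LV leads.

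**Conclusion.** The concern holds as a cheap improvement to measurement, not as a flaw that invalidates the endpoints. The choice of method is a stated permission, given afresh at each test, and the visible text does not tie the 1-month method to the pre-scan one. The own-control argument in protocol 14.2 needs a constant measurement process, which the procedures do not secure.

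The size depends on assumptions that the documents cannot settle: the reading error, the offset between methods, and how often and in which direction leads switch. With independent choice of method, the assumed 0.25 V offset adds roughly one or two false failures among 70 RA/RV leads and slightly raises the chance of missing a 0.6 V rise. Only consistent one-way switching brings the large effects. If sites keep one method there is no effect.

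**What to change.** In protocol 8.4.4.4, 8.4.4.6 and 8.4.4.7.1, add that the method used for each lead at pre-scan testing is to be used again at post-scan and 1-month testing where feasible. If it cannot be, the reading is taken by the other method and kept. The feasibility clause matters because protocol 8.2.2 analyses only subjects with complete data and 17.1 rules out waivers, so an absolute rule could turn usable readings into missing values or deviations.

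Record the method for each reading, if the case report form does not already do so. In the SAP, show both effectiveness proportions with and without mixed-method leads, if the redacted text does not already provide this.

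The cost is one sentence in each of three sections, possibly one form field, one small sensitivity display, and less freedom for sites in choosing a test method.
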